## 1.0 Objectives / Specific Aims

The purpose of this project is to establish initial feasibility and tolerability of a combined aerobic exercise (AEx) and upper extremity motor practice intervention on upper extremity (UE) function in chronic stroke survivors. This novel intervention pairs AEx with a virtual reality-based upper extremity rehabilitation game, Duck Duck Punch (DDP). While response to UE rehabilitation interventions, such as DDP, involves a multitude of factors, neuroplastic changes are a primary mechanism underlying functional recovery. AEx has been shown to improve overall brain function and promote a neuroplastic environment; thus it may serve as an effective ‘primer’ and enhance the effects of DDP. Movement-based priming for neurorehabilitation involves performing movement or exercise before, or concurrent to, a therapeutic intervention with the goal of improving the efficacy of the therapeutic intervention. Emerging evidence supports AEx as a potential priming tool for UE stroke rehabilitation. AEx combined with UE task training can improve UE function and self-reported health status in chronic stroke survivors. Despite the promising results, there are gaps in the literature involving: 1) the clinical applicability of an AEx priming session; and 2) mechanisms contributing to changes in UE functions in response to AEx-primed UE rehabilitation. Addressing these gaps will be necessary to develop an AEx primer that is potent and time efficient, with respect to current clinical models. Therefore, the purpose of this pilot proposal will be to establish initial feasibility and tolerability benchmarks for the AEx + DDP intervention.

Aim 1: Demonstrate the feasibility of pairing AEx + DDP in stroke survivors with UE hemiparesis.

*Outcomes for Aim 1:* The primary objective of this project is to demonstrate feasibility and tolerability of this novel intervention. Metrics including recruitment, adherence, acceptability, retention, and adverse events will be examined to assess the feasibility and tolerability of AEx + DDP. Recently Valkenborghs and colleagues (2019) reported rates of 93% adherence, 95% retention, and 100% acceptability among 9 stroke survivors participating in a similar dual intervention. We will use these benchmarks to determine the feasibility and tolerability of AEx+DDP.

Aim 2: Quantify the magnitude of the effect of AEx + DDP intervention on UE impairment and function.

*Outcomes for Aim 2:* Two objective outcome measures, Fugl-Meyer Upper Extremity Assessment (FMA-UE) and Wolf Motor Function Test (WMFT), will be used to assess upper extremity impairment and function. This data will compared to historical controls from previous DDP trials from [name] (Co-I) lab.

Aim 3: Examine the relationship of biomarkers of neuroplasticity (BDNF and corticomotor excitability) and response to AEx + DDP.

*Outcomes for Aim 3:* We have selected transcranial magnetic stimulation (TMS)-based and blood-based measures to assess the neuroplastic potential of each subject as well as the acute effects of AEx+DDP on biomarkers of plasticity. These assessments will provide important data describing the neuroplastic potential of each subject (potential responders vs. non-responders) and the acute effect of AEx and DDP on indices of neuroplasticity.

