## 4.0 Inclusion and Exclusion Criteria/ Study Population

**Eligibility screening:** Subjects (male and female), ages 21-90, will be screened and recruited for the study six months to ten years post-stroke, allowing for natural recovery during the first 6 months post-stroke. The pool of candidates for the study will be recruited from the database registry supported by the Clinical and Translation Tools and Resources (CTTR) Core of the NIH-funded Center of Biomedical Research Excellence (COBRE) in Stroke Recovery at MUSC.. Eligible participants will be screened for participation and if appropriate will be accepted into the study.

**Inclusion criteria:** 1) experienced unilateral stroke at least 6 months, but no more than 120 months prior; 2) voluntary shoulder flexion of the affected arm  $\geq 20^\circ$  with simultaneous elbow extension  $\geq 10^\circ$ ; 3) moderate arm movement impairment (UE Fugl-Meyer Assessment  $> 21$  but  $< 52$  points; 4) passive range of motion in paretic shoulder, elbow, wrist, thumb and fingers within 20 degrees of normal; 5) 21-90 years of age; 6) ability to communicate as per the therapists' judgement at baseline testing; 7) ability to complete and pass an exercise tolerance test.

**Exclusion criteria:** 1) lesion in brainstem/cerebellum as these may interfere with visual-perceptual/cognitive skills needed for motor re-learning; 2) presence of other neurological disease that may impair motor learning skills; 3) orthopedic condition or impaired corrected vision that alters reaching ability (e.g., prior rotator cuff tear without full recovery); 4) paretic arm pain that interferes with reaching; 5) unable to understand or follow 3-step directions; 6) severe cognitive impairment (Montreal Cognitive Assessment score  $< 22$ ); 7) severe aphasia; 8) inability to read English, 9) history of congestive heart failure, unstable cardiac arrhythmias, hypertrophic cardiomyopathy, severe aortic stenosis, angina or dyspnea at rest or during ADL's; 10) Severe hypertension with systolic  $> 200$  mmHg and diastolic  $> 110$  mmHg at rest; 11) history of, or current, depression; **and for brain stimulation procedures only:** 12) women of child-bearing potential; 13) electronic or metallic implants; 14) history of seizures.

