### Screening and assessment visits

**Screening Assessments:** Following informed consent procedures we will perform screening assessments. Participants will be screened for cognitive function and depression with the Montreal Cognitive Assessment and Patient Health Questionnaire.

- **Montreal Cognitive Assessment (MoCA):** The MoCA is 30-point test used for assessing cognitive impairment. It assesses short-term memory recall, attention and concentration, executive function, language, visuoconstructional skills, orientation, and calculations. Subjects demonstrating cognitive impairment, indicated by a MoCA score < 22 will be excluded.
- **Patient Health Questionnaire (PHQ-9):** The PHQ-9 is a 9-item instrument used for screening and monitoring depression. Since depression has been shown to impact neuroplastic potential, subjects with depression (PHQ-9 > 4) will be excluded.
- **Transcranial Magentic Stimulation (TMS) Screen:** The TMS Screen has been developed from safety guidelines to ensure patients and study participants are safe to receive TMS. If the TMS screen identifies one or more contraindications to TMS subjects will be excluded from receiving TMS assessments.

**Clinical Assessments:** We will perform clinical assessments of UE impairment (FMA-UE), UE function (WMFT), and 'real world' arm use (SIS). This assessment battery is standard to most post-stroke rehabilitation trials. These data will help describe the functional status of participants. A licensed physical therapist, exercise physiologist, or trained study personnel through the South

Carolina Center for Stroke Recovery Research will perform all assessments. These assessments will be performed pre- and post-intervention (Pre Visit 1 and Post Visit 1).

- **Fugl Meyer Upper Extremity Assessment (FMA-UE):** The FMA-UE is a 33-item measure of UE impairment; however, the 3 items testing reflex response will not be administered because they do not measure a voluntary movement construct. Assessments will be video recorded and scored from the videos by trained, blinded raters. Each item will be scored on a 3-point rating scale (0=unable, 1=partial 2=near normal performance), item ratings will be summed and reported out of 60 points so that larger numbers indicate greater UE motor ability. The FMA-UE will be video recorded to allow for scoring by a blinded reviewer.

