- **Wolf Motor Function Test (WMFT):** The WMFT is a 15-item measure of UE functional ability. The WMFT will be administered in a standardized manner according to lab specific procedures. Assessments will be video recorded and scored from the videos by trained, blinded raters. Performance of each item will be timed (seconds) and the average time to perform items will be reported so that lower values indicate greater UE function.
- **Stroke Impact Scale (SIS):** The SIS assesses physical function as well as other dimension of health-related quality of life: emotion, communication, memory & thinking, and social role function. Specifically, the Hand and Perceived Recovery subsets of the SIS will be used to assess the effect of the intervention on 'real world' arm use. The SIS-hand consists of 5-items regarding difficulty of paretic hand use during everyday tasks during the previous two weeks. Items will be rated on a 5-point scale (5=not difficult, 1=cannot do) and reported as an average item rating. The SIS-recovery subtest is a single-item in which the participant rates his/her perceived post-stroke recovery from 0%-100% recovered.
- **International Physical Activity Questionnaire (IPAQ):** The IPAQ is a 5-part self-administered physical activity seven-day recall. The IPAQ assesses physical activity frequency, duration, and intensity over the previous seven days in four domains: (1) job-related, (2) transportation, (3) housework and family caring, recreation, (4) sport and leisure. In addition, the fifth domain assesses time spent sitting at work, at home, and during leisure time. The IPAQ has been shown to produce reliable results and validity has been established against accelerometer measurement of physical activity. It is also easily implemented and appropriate for broadly defining physical activity habits.

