## Neurophysiological Assessments

- **Assessment of neuroplastic potential:** Participants' neuroplastic potential will be assessed with a plasticity-inducing paradigm called Paired Associative Stimulation (PAS). Briefly, PAS utilizes a repeated and timed peripheral nerve stimulation combined with transcranial magnetic stimulation (TMS) of the contralateral motor cortex to induce motor cortex plasticity. Prior to- and after PAS, corticomotor excitability (CME) is assessed via motor evoked potentials (MEP) which are obtained by single pulse TMS and electromyography (EMG) of a contralateral peripheral muscle. PAS will be assessed pre- and post-intervention (Pre Visit 3, Post Visit 2). PAS will be assessed in the ipsilesional motor cortex and paretic UE.
- **Paired Associative Stimulation:** Prior to PAS, all participants will be assessed for potential contraindications to TMS using a safety-screening questionnaire. First, we will use a combination of on-line surface electromyography (sEMG) recordings to view peak-to-peak motor evoked potential (MEP) amplitude and a neuro-navigation system to identify the optimal coil position for stimulation of the abductor pollicis brevis (APB) muscle (APB 'hotspot'). The area on the hand knob of the motor cortex that produces the largest and most consistent MEP's of the APB muscle will be marked as the 'hotspot' using the neuro- navigation system. We will then assess baseline cortical excitability by collecting a 'bin' of twenty test MEP's and a standardized stimulation intensity. This stimulation intensity will remain the same throughout the experimental session in order to allow for comparisons of MEP amplitude before and after PAS. After assessment of cortical excitability participants will receive PAS. For PAS, participants will receive a combination of simultaneous peripheral nerve stimulation and brain stimulation. Stimulation of the median nerve will be delivered via constant current stimulator (DS7A; Digitimer, Hertfordshire, UK) just proximal to the wrist. Bipolar electrodes will deliver a 200 $\mu$ s square wave pulse at an intensity equal to 300%

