**Statistical Analysis Plan:** Feasibility and tolerability metrics of adherence, retention, and acceptability will be assessed (Aim 1). FMA-UE, WMFT, and SIS data will be compared to historical control data from previous DDP trials from [name] lab (Aim 2). We will utilize ANOVAs to test the effect of adding AEx to DDP on the mean FMA-UE, WMFT, and SIS-hand item rating and the average SIS-recovery scores (PROC GLM, SAS v9.4). Additionally, data describing the effect of AEx+DDP on UE impairment and function will be used to generate effect sizes for future research proposals. Pre- and post intervention PAS assessment will be tested with a student's T-test or Wilcoxon rank-sum test based on distributional assessment. The acute (within session) and training (over the course of intervention) effect of AEx on BDNF and DDP on CME will be assessed with a generalized mixed model analysis (PROC MIXED). Relationships of biomarkers of plasticity (PAS, BDNF, CME) and response to AEx+DDP (change in FMA-UE or WMFT) will be explored with Pearson or Spearman-rank order correlational analysis, depending on distributional assessment (Aim 3).

**Confidentiality:** All records regarding participation in this study will be kept in locked file cabinets in the appropriate laboratories and/or offices, and stored on MUSC network storage. Access to linked identifiers is limited to research personnel intimately involved with the human subjects. All data and records acquired from subjects is for research purposes only and will be kept confidential and maintained in a secure database identifiable only by subject code. The results of the study may be published for scientific purposes; however, subjects' identities will not be revealed and data will not be traceable to any individuals in any resultant publications. The information gathered during this study will be kept confidential to the extent permitted by law.

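### The Aim 3 correlations use raw change scores without baseline adjustment; adding a baseline-adjusted value for PAS and CME against FMA-UE change is a cheap safeguard against bias of unknown direction

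*Combined protocol and SAP*

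**What the plan says.** Section 1.0 sets Aim 3 as follows: "Examine the relationship of biomarkers of neuroplasticity (BDNF and corticomotor excitability) and response to AEx + DDP". It hopes the biomarkers will help describe who might or might not respond. The method is in section 11.0, Statistical Analysis Plan, where the relation of PAS, BDNF and CME to "response to AEx+DDP (change in FMA-UE or WMFT) will be explored with Pearson or Spearman-rank order correlational analysis". No baseline covariate, partial correlation or adjusted change score is mentioned there or elsewhere.

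Three other places bear on this:
- **Entry range** (section 4.0): "UE Fugl-Meyer Assessment $> 21$ but $< 52$ points", that is 22 to 51 in whole points. The scale maximum for this criterion is not stated.
- **Outcome scale** (section 9.0, Clinical Assessments): the reflex items are dropped and "item ratings will be summed and reported out of 60 points so that larger numbers indicate greater UE motor ability". WMFT is a time in seconds: "the average time to perform items will be reported so that lower values indicate greater UE function". Both are measured before the intervention, at Pre Visit 1.
- **Biomarkers** (section 9.0, Neurophysiological Assessments): "PAS will be assessed in the ipsilesional motor cortex and paretic UE". CME around DDP sessions is also recorded in the paretic arm. BDNF is a blood measure.

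**The concern.** A raw change score carries its baseline with it. A participant who enters near the top of the FMA-UE range has little room to gain, and measurement error in the baseline enters the change with a negative sign. If a biomarker also varies with baseline impairment, a two-variable correlation mixes two things: how plastic the participant is, and how impaired the participant was at entry.

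Depending on the signs, this can shrink a real link, inflate it, or produce one where none exists at a given baseline. The pilot is meant to inform later trials of exercise priming, and an ambiguous correlation would be carried into them. The data needed to separate the two readings are already collected.

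**Working it through.** **The plan's own figure.** The only sample-size calculation is for the Aim 2 comparison: difference 7.9, pooled SD 4.25, 80% power, alpha 0.05. By the normal approximation, two-sided, n = 2 × (1.960 + 0.842)² × 4.25² / 7.9² = 2 × 7.85 × 18.06 / 62.41 = 4.5, rounded up to 5 per group. The stated n=5 reproduces. No power or precision is given for the Aim 3 correlations.

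**Room to change on FMA-UE.**
- At entry score 22: 60 − 22 = 38 points. At 51: 60 − 51 = 9 points.
- The cited mean gain of 12.3 is out of reach above 60 − 12.3 = 47.7, so for entry scores 48 to 51.
- If the entry limits are on a 66-point scale (33 items × 2), the room is 44 down to 15 points and the mean gain is always reachable.

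**How much correlation the ceiling alone creates.** Assume entry scores spread evenly over 22 to 51 and gains normal with mean 12.3 and SD 4.25 (the plan's pooled SD), cut off at the maximum. On 60 points about 14% of participants are capped and the baseline-change correlation is about −0.18. On 66 points about 3% are capped and it is about −0.02. An assumed FMA-UE measurement error of 2 to 3 points would move the 60-point value to about −0.25 to −0.31.

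**Effect on the planned correlation.** Let M be the biomarker, B baseline, C change and r_p the correlation of M and C at fixed baseline. Then

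r(M,C) = r(M,B) × r(C,B) + r_p × √[(1 − r(M,B)²)(1 − r(C,B)²)]

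The documents do not give r(M,B), so +0.3 and +0.5 are assumed. With r(C,B) = −0.18 and r_p = 0.7:
- r(M,B) = 0.3: −0.054 + 0.7 × √(0.91 × 0.9676) = −0.054 + 0.657 = 0.60
- r(M,B) = 0.5: −0.090 + 0.7 × √(0.75 × 0.9676) = −0.090 + 0.596 = 0.51

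With r(C,B) = −0.02 the same steps give 0.66 and 0.60. At r(M,B) = 0.5, then, about half of the fall from 0.70 to 0.51 comes from the ceiling. The rest arises because the biomarker shares variation with baseline.

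**Rejection rates.** Trivariate-normal simulation, n=10, two-sided 5%, testing simple r on n − 2 df and partial r on n − 3 df:

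| r(M,B) | r(C,B) | True r_p | Unadjusted | Adjusted |
|---|---|---|---|---|
| +0.3 | −0.18 | 0.7 | 49% | 62% |
| +0.5 | −0.18 | 0.7 | 34% | 62% |
| 0 | −0.18 | 0.7 | 66% | 62% |
| 0 | 0 | 0.7 | 68% | 62% |
| +0.5 | −0.18 | 0 | about 6% | 5% |
| +0.5 | −0.5 | 0.7 | 12% | 62% |
| +0.5 | +0.5 | 0.7 | about 82% | about 61% |
| +0.5 | −0.5 | 0 | 10.5% | 5% |
| +0.7 | −0.7 | 0 | 31% | 5% |

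The first five rows use the ceiling-only correlation or none. The last four need baseline-change correlations that the documents do not supply.

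**Cost of adjusting.** Critical |r| = t/√(t² + df). At n=10 it is 2.306/√(5.318 + 8) = 0.632 unadjusted and 2.365/√(5.593 + 7) = 0.666 adjusted. At n=8 (10 less the planned 20% dropout) it rises from 0.707 to 0.754.

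**The case against.** The strongest reply is that the large distortions are assumed. The ceiling is the only mechanism whose size can be worked out from the plan's figures, and it gives −0.18 at most without added measurement error. That stands. A reader might infer that the unadjusted analysis would produce false links in 10% to 31% of such studies. The documents do not support this: those rates need correlations of 0.5 to 0.7 in size on both sides, and at −0.18 the rate stays near 6%.

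The biomarker-baseline link is also unproven. PAS response and the CME change around DDP are before-and-after comparisons within a session, not raw MEP size. Measurement in the paretic limb makes a link with impairment plausible but fixes neither its sign nor its size. This too stands. A reader might infer that the bias must hide a real link, but with both baseline correlations at +0.5 the raw correlation is inflated instead.

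Nor do all biomarkers and outcomes share the problem equally. No route from baseline impairment to BDNF is offered in the documents, and adjusting there at −0.18 lowers power from 66% to 62%. WMFT is a time, and no limit comparable to the 60-point ceiling is shown for it.

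Finally, the analysis is exploratory, feasibility is the primary objective, and no decision rule depends on these correlations. That lowers the stakes. It does not remove the ambiguity in what a reported correlation means.

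**Conclusion.** The point holds in a limited form. Aim 3 leaves the collected baseline scores out of its correlations, and for PAS and CME against FMA-UE change the result can be biased in either direction.

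On the plan's own figures the risk of a false link is slight. The material risk is a missed one: power of 49% to 34% against 62% at n=10. That figure rests on four assumptions: a biomarker-baseline correlation of +0.3 to +0.5, a true partial correlation of 0.7, a 60-point scale for the entry limits, and evenly spread entry scores. On a 66-point scale the ceiling's contribution nearly vanishes.

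The documents do not support a claim that every planned correlation is invalid or should be replaced. Adjustment also does not cure imprecision: an adjusted correlation of 0.67 at n=10 has a 95% CI of about 0.01 to 0.92, and at n=8 the interval includes zero. TMS exclusions could reduce the numbers further.

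**What to change.** Add one sentence to the Statistical Analysis Plan in section 11.0. Beside each planned correlation of PAS and CME with FMA-UE change, report the partial Pearson or Spearman correlation adjusted for baseline FMA-UE, with a 95% CI. Regressing the post score on its baseline plus the biomarker is an alternative. State that a link will be read as specific to the biomarker only if the adjusted value supports it. Keep the unadjusted value in the report. Doing the same for WMFT and BDNF is optional, because the case there is weaker. It would also help to state whether the entry limits in section 4.0 are on the 60-point score.

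No new data are needed. The price is one degree of freedom, and a power loss from 68% to 62% at n=10 (true correlation 0.7) if baseline turns out to be unrelated to both biomarker and change. Reporting both values keeps that loss visible.

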## 2.0 Background

With a surviving cohort of nearly 7 million individuals, stroke is the leading cause of long-term disability in the United States. Of the ~795,000 new strokes occurring annually, approximately

2/3rds of survivors will have some degree of long term disability. The prevalence of post-stroke disability coupled with the fact that more people are surviving stroke reflects an increasing need to develop effective rehabilitation strategies aimed at reducing disability and improving quality of life for the millions of stroke survivors, their families and caregivers.

The overwhelming majority of stroke survivors, >75%, exhibit upper extremity (UE) hemiparesis, and only 15% will recover fully. Furthermore, residual UE impairment is closely linked to long-term disability and reduced quality of life. Current meta-analytic evidence supports virtual reality stroke rehabilitation interventions for improving UE function suggesting that this is a promising area for further therapeutic development. Our team (Co-I: [name]) has developed an innovative virtual reality stroke rehabilitation game, Duck Duck Punch (DDP). DDP is an interactive computer game deliberately designed to enhance UE movement quality via individualized progressive movement practice along with an array of performance metrics allowing for within-session feedback on movement performance. Although response to UE virtual reality rehabilitation interventions, such as DDP, involves a multitude of factors, neuroplastic changes are a primary mechanism underlying functional recovery. Thus, pairing DDP with a priming intervention to facilitate a ‘neuroplastic-friendly’ environment may make the CNS more amenable, and enhance response to DDP rehabilitation and ultimately improve outcomes.

Aerobic exercise (AEx) training has positive benefits on overall brain function including enhanced global cognition, executive function, and processing speed and attention in healthy, older adults. Additionally, a single session of AEx acutely improves motor memory and learning in younger, healthy adults. Although AEx has been used to improve cardiovascular function following stroke, its neurofacilitatory effects in stroke have yet to be tested empirically. Candidate mechanisms through which AEx enhances brain function and motor learning include changes in circulating brain-derived neurotrophic factor (BDNF) and corticomotor excitability. BDNF is believed to play an integral role in several neuroplastic processes and promotes the strengthening of synaptic connections, i.e. long-term potentiation (LTP) and current research indicates that AEx can acutely and chronically increase circulating BDNF. Corticomotor excitability (CME) is often used as an indicator of LTP-like neuroplasticity and may underlie improvements in motor memory and learning. Similarly to BDNF, AEx can acutely enhance corticomotor excitability in control and chronic stroke subjects. Facilitating central nervous system function provides rationale to determine the role of AEx in ‘priming’ the brain for a subsequent intervention to maximize neuroplastic potential.

